7.2 Adverse event reporting

IBCSG 24-02 (SOFT: Suppression of Ovarian Function Trial) V3.0 Amendment 2 14July11 Amendment 1: blue text; Amendment 2: green text

The main criterion for tolerability is the occurrence of toxicities and adverse events. The severity and causality will be classified according to the NCI Common Terminology Criteria for Adverse Events (CTCAE). The CTCAE should be labeled: CTCAE Version 3.0. The CTCAE is available for downloading on the internet at (http://ctep.cancer.gov/reporting/ctc.html).

An adverse event is defined as any untoward medical occurrence that occurs from the first dose of study medication until 30 days after the final dose, regardless of whether it is considered related to a medication.

In addition, any known untoward event that occurs subsequent to the adverse event reporting period that the investigator assesses as possibly related to the protocol treatment should be considered an adverse event.

Symptoms of the targeted cancer (if applicable) should not be reported as adverse events.

The toxicity severity grade provides a qualitative assessment of the extent or intensity of an adverse event, as determined by the investigator or as reported by the subject. The severity grade does not reflect the clinical seriousness of the event, only the degree or extent of the affliction or occurrence (e.g. severe nausea, mild seizure), and does not reflect the relationship to study drug.

Severity grade for other adverse events, not covered in the toxicity grading scale:

1 = Grade 1	Mild
2 = Grade 2	Moderate
3 = Grade 3	Severe
4 = Grade 4	Life-threatening
5 = Grade 5	Fatal

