### TEXT Schema:

\* Randomization prior to receiving any adjuvant systemic therapy

\*\*CT (chemotherapy) is determined by investigator/patient choice and if used, should begin at the same time as triptorelin.

[figure not shown]
\*\*\*Tamoxifen or exemestane should start after adjuvant chemotherapy has been completed or approximately six to eight weeks after the initiation of triptorelin, whichever is later.

IBCSG 25-02 (TEXT) is an international, non-blinded, randomized phase III trial designed to investigate the efficacy the aromatase inhibitor (AI) exemestane with OFS, achieved by long-term use of GnRH analogue, compared with tamoxifen+OFS. TEXT focuses the AI question on premenopausal patients whom the physician feels OFS is most appropriate from the start of adjuvant therapy. Eligibility required enrollment within 12 weeks of definitive surgery and excluded patients who had already received any (neo)adjuvant chemotherapy or endocrine therapy. Randomization used 1:1 allocation and stratified by whether adjuvant chemotherapy was planned (no; yes), and number of positive nodes (0; 1 or more). Patients would either receive no chemotherapy or commence chemotherapy at the same time as GnRH analogue is initiated. Patients had to use GnRH analogue for at least 6 months and then could change to permanent OFS with surgery or radiation at any time thereafter.

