### SOFT Schema:

\* Patients may have received tamoxifen or an anti-aromatase agent prior to randomization

\*\* OFS = ovarian function suppression (triptorelin for 5 years OR surgical oophorectomy OR ovarian irradiation)

IBCSG 24-02 (SOFT) is an international, three-arm, non-blinded, randomized phase III trial designed to investigate the role of OFS and the role of the AI exemestane, originally planned with three primary comparisons: tamoxifen+OFS versus tamoxifen alone; exemestane+OFS versus tamoxifen alone; and exemestane+OFS versus tamoxifen+OFS. SOFT focuses the OFS question on those who biologically would be most likely to benefit, i.e., women with endocrine-responsive breast cancer with premenopausal status either after completion of (neo)adjuvant chemotherapy or following surgery alone.

Eligibility required enrollment either: (a) within 8 months of the final dose of chemotherapy once premenopausal status was confirmed by estradiol levels (e.g., patients with temporary chemotherapy-induced amenorrhea who regained premenopausal status within 8 months were eligible); or (b) within 12 weeks of definitive surgery if no adjuvant chemotherapy was to be given. Patients could have received adjuvant oral endocrine therapy (but not GnRH analogues) for up to 8 months prior to randomization. The 8-month criterion was an early protocol amendment (from 6 months) to overcome logistical challenges of enrolling a patient who presented after regaining premenopausal status at a 6-months post-chemotherapy standard-of-care visit.

Randomization used 1:1:1 allocation, and was stratified according to prior (neo)adjuvant chemotherapy (yes;no), lymph node status (0; 1+) and intended method of OFS (GnRH analogue, oophorectomy; ovarian irradiation). For patients randomized to receive OFS, the use of GnRH analogue, bilateral oophorectomy or bilateral ovarian irradiation was by patient preference and patients who began with GnRH analogue could opt to undergo surgery or irradiation at any time.

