### 2.6.5.2 AE analysis

Targeted AEs, and other grade 3-5 AEs, are collected on CRFs, until 1 year after the cessation of all protocol treatment. The grade and causality attribution are recorded according to the NCI Common Terminology Criteria for Adverse Events (CTCAE) version 3.0. In TEXT, chemotherapy-related AEs are collected separately.

The targeted AEs will be summarized by AE type and maximum grade over time, regardless of causality attribution. The maximum grade consolidates the reports of a given type of AE for a patient over time since randomization (i.e., baseline reports are excluded) by taking the maximum across time (i.e., a patient appears only once for a given type of AE). Patients with reports of multiple AEs of different types are reported multiple times under the relevant AE categories. Maximum grade 0 indicates that the AE type has not been reported.

Note, during a period of trial conduct, the IBCSG audit team was asking sites to record grade 3+ weight gain and obesity as other AEs; discussed among StatC/DMC/CC that CRFs record weight serially on E-form and any analysis of weight changes and/or obesity [in these or other IBCSG adjuvant trials] would use the actual weight, not the AE; as a result the audit team changed their practice. Therefore the weight change and obesity “other grade 3+” AEs will be deleted from dataset before summarizing other grade 3+ AEs because the incidence will not be interpretable.

Tables:

- AI Question (E+OFS vs T+OFS)
  - Targeted AEs reported according to treatment group (N; %)
  - Targeted AEs reported according to trial & treatment group (N;%)
  - Targeted AEs reported according to cohort & treatment group (N;%)

- Tables above repeated for the subset of events deemed possibly, probably or definitely related to study treatment(s)
- SOFT (E+OFS vs T+OFS vs T)
  - Targeted AEs reported according to treatment group (N; %)
  - Targeted AEs reported according to chemo strata & treatment group (N;%)
  - Tables above repeated for the subset of events deemed possibly, probably or definitely related to study treatment(s)

Other grade 3 or higher AEs are also requested on CRFs, by write-in text. All will be tabulated, similarly according to max grade, but the intention is to focus on those deemed possibly, probably or definitely related to study treatment(s), which will also be tabulated.

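### For non-targeted grade 3 or higher adverse events the SAP puts the emphasis on the treatment-related subset, the reverse of its rule for targeted events and open to attribution bias in non-blinded trials

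*SAP*

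**What the plan says.** SAP 2.6.5.2 sets two rules.

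- **Targeted events.** "The targeted AEs will be summarized by AE type and maximum grade over time, regardless of causality attribution". The listed tables are split by treatment group, and in addition by trial and cohort or by chemotherapy stratum. Related-only versions are repeats of these tables.
- **Other events.** "Other grade 3 or higher AEs are also requested on CRFs, by write-in text". The rule for these starts out inclusive: "All will be tabulated, similarly according to max grade". The same sentence then turns to the related subset and says where the weight will fall: "but the intention is to focus on those deemed possibly, probably or definitely related to study treatment(s), which will also be tabulated". The listed by-arm tables name targeted events only, and the text does not say outright that the all-cause table of other events is split by arm.

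The SAP describes SOFT as an "international, three-arm, non-blinded, randomized phase III trial" and TEXT likewise as non-blinded. Protocol 7.2 defines an adverse event "regardless of whether it is considered related to a medication". Protocol 7.3.1, in the section on serious events, defines a related event by the investigator's assessment. Protocol 7.3.3 has the Coordinating Center review causality for serious events; no such review is described for other events.

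**The concern.** Write-in events are where, within the planned adverse event tables, toxicity outside the targeted list can appear. That is also where attribution is least reliable, because an effect nobody expects is unlikely to be called related. Focusing on the related subset gives least weight to the events this category is best placed to reveal.

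The second problem is comparability. Randomization protects a comparison of all events, but not a comparison of events filtered by a judgement made with the assignment known. On the OFS arms there are two treatments to which an event can be attributed; on tamoxifen alone there is one. If attribution rates differ for that reason, the related-only contrast can show a difference where none exists or shrink a real one. The SAP gives no reason for reversing the rule it uses for targeted events.

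**Working it through.** **Text check.** There is no figure in the plan to reproduce, so the rules are set side by side.

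| | Targeted events | Other grade 3+ events |
|---|---|---|
| All-cause table planned | Yes | Yes |
| Split by arm stated | Yes | Not stated outright |
| Related-only table planned | Yes, as a repeat | Yes |
| Stated emphasis | All-cause | Related-only |
| Test between arms planned | No | No |

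The difference lies in the last column: the emphasis is reversed, and the all-cause display is the less fully specified one.

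**Illustration of size, on assumed rates.** SAP 1.3.2 gives 2,033 patients in the two tamoxifen arms of SOFT, so n = 2033/2, about 1,016 per arm. This slightly overstates n, because the adverse event population is a subset of ITT. Incidence and attribution rates are assumptions; the documents give none.

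With true incidence p and attribution fraction a, the related-only rate is p × a. SE = √{[p₁(1−p₁) + p₂(1−p₂)]/n}. The chance of nominal two-sided p<0.05 is about Φ(|p₁−p₂|/SE − 1.96).

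*Equal true incidence, unequal attribution:*

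| True incidence, both arms | Attribution | Related-only rates | Ratio | Chance of p<0.05 |
|---|---|---|---|---|
| 2% | 40% v 60% | 0.8% v 1.2% | 1.5 | 15% |
| 5% | 40% v 60% | 2.0% v 3.0% | 1.5 | 30% |
| 10% | 40% v 60% | 4.0% v 6.0% | 1.5 | 54% |
| 2% | 30% v 60% | 0.6% v 1.2% | 2.0 | 30% |
| 5% | 30% v 60% | 1.5% v 3.0% | 2.0 | 63% |
| 10% | 30% v 60% | 3.0% v 6.0% | 2.0 | 90% |

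Worked line (10%, 40% v 60%): SE = √[(0.04×0.96 + 0.06×0.94)/1016.5] = 0.0097; 0.02/0.0097 = 2.07; Φ(2.07 − 1.96) = 0.54.

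With 40% v 50% attribution the chances are 7%, 12% and 19% at 2%, 5% and 10% incidence.

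*True doubling from 2% to 4%, same attribution in both arms:* the chance of nominal p<0.05 is about 75% on all events, 46% if half are attributed, and 21% if one fifth are attributed. The relative risk stays at 2; what is lost is the number of events.

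In every row the all-cause table is unaffected by attribution.

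**The case against.** The strongest reply is that the sentence on other events opens by saying all of them will be tabulated. A reader who sees only the second half might infer that comparisons between arms depend on attribution, or that unrelated events disappear. The documents do not support that: the all-cause tabulation is planned, nothing is dropped because of attribution, and no test between arms is planned. This stands, and it limits the point to emphasis.

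A reader might also infer that write-ins are the only way unexpected harm can surface. That goes too far.

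- Serious events are reported by seriousness (Protocol 7.3.1) and centrally reviewed (7.3.3).
- The DSMC monitors toxicity at its semi-annual meetings (Protocol 9.5).
- Second malignancies as first failure and deaths without a prior cancer event are summarized by treatment group without an attribution filter (SAP 2.6.4).

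Within this report's adverse event tables, however, the point keeps some force. The SAP lists no table of serious events, and SAP 2.6.5.3 leaves post-treatment events on the follow-up form out of the update.

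Protocol 5.2.3 names visual disturbances and diarrhea as more common with exemestane, and neither is targeted. They are weak examples. They were already known, so they are likely to be called related, and nothing says they reached grade 3.

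The argument of two agents against one applies to OFS against tamoxifen alone. In the AI Question both arms receive OFS plus one oral agent. Also, 2.6.5.2 does not itself say who attributes causality; the investigator definition comes from the protocol's section on serious events.

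The larger probabilities belong to a pooled composite at 10% incidence. Tabulation by event type would involve lower rates, where the 2% rows are the more relevant. Finally, a noisy all-cause table of mixed free-text events is a fair reason to want a filtered view; it supports keeping the related-only table, but not leading with it.

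**Conclusion.** The point holds as one of emphasis. For other grade 3 or higher events the SAP commits its interpretation to the table that depends on non-blinded attribution, although it plans a table that does not and uses that kind of table first for targeted events. The risk of distortion is mainly in OFS against tamoxifen alone. The loss of weight for unexpected effects applies to all comparisons.

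The practical reach is limited. Cardiac, cerebrovascular, thrombotic, hypertensive, bone and glucose events are on the targeted list (Protocol 7.1, note C) and are summarized regardless of causality. The size cannot be known from the documents: a spurious ratio of 1.5 needs attribution of 40% against 60%, and it vanishes if attribution is equal. The conclusion rests on the investigator definition of relatedness also governing the adverse event form, which the documents imply but do not state.

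**What to change.** In SAP 2.6.5.2, replace the statement of intention with a sentence saying that other grade 3 or higher events will be tabulated by treatment group and maximum grade regardless of attribution, that this table is the main display for comparing arms, and that the related-only table is supportive. It would also help to state who makes the attribution on the adverse event form.

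The cost is one sentence and an explicit split by arm; both tabulations are already planned and no new data are needed. The downside is more background noise in the main table.

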### 2.6.5.3 Post-treatment AEs

The follow-up (E) form collects some events occurring after protocol treatment has ended (which aren't reported on the AE form): clinically-significant cardiovascular and/or cerebrovascular events, bone fractures, and other severe ( $\geq$  grade 3) AEs. **These will not be part of the update clinical trial report.**

## 2.6.6 Treatment

### 2.6.6.1 Protocol treatment

Data are from the internal Treatment Summary form; see SDMC Treatment Summary Form Guidelines for details of how data are recorded. **There is some inconsistency, relevant primarily for TEXT, among patients who completed 5 years of oral ET with whether any oral ET that continued after 5y since randomization but stopped within year 5-6 was recorded on the protocol treatment page or non-protocol treatment page (i.e., though protocol said 5 yrs since randomization, patients sometimes received 5 yrs since oral ET start; goal is to separate completion of 5 yrs of oral ET from extended adjuvant ET). Guidelines originally said put it all on non-protocol treatment page but this was changed so that up to 6 additional months stayed on protocol treatment page, and if it continued beyond 6 months then protocol treatment ended on day rando+5y and non-protocol treatment started on day rando+5y+1d until actual stop date. So need to be careful in analysis of time until oral ET stop that everything is consistently truncated at 5 yrs.**

As of the clinical data cut-off, all patients would have ceased protocol treatment (there are a few patients for whom final confirmation of cessation not received and/or final date of cessation not documented). Protocol treatment status will be summarized, overall and by treatment assignment, and also by trial and/or cohort. The variables are the same as in the original trial report (see original SAP for details), with the exception of the “continuing protocol treatment” category vs. “last known on protocol treatment” categories.

### 2.6.6.2 Non-protocol treatment

**This will not be part of the update clinical trial report.** **A preliminary analysis will be conducted after compiling the update clinical trial report to get a sense of what is going on; a full analysis of protocol and non-protocol treatment is planned to follow separately.** We will plan to describe

- Non-protocol ET to complete 5 years (if protocol-assigned T/E is stopped early);
- [OFS question] Use of OFS within 5 years of randomization among patients assigned tamoxifen-alone

- Concomitant bisphosphonates use
- Extended adjuvant ET use, including oophorectomy/ovarian irradiation after 5 years.

As noted above, among those who completed 5 yrs of protocol-assigned oral ET, need to be careful about an extra few months up to 1 yr of protocol-assigned oral ET, which could be reflected either in the protocol treatment variables or non-protocol treatment variables. And need to be careful not to consider these few extra months as extended adjuvant ET.

Recall, protocol treatment is considered as completed per-protocol at the time of any DFS event. In the case of local recurrence and second (non-breast) cancer, the protocol allowed treatment to continue. The Treatment Summary form non-protocol therapy page captures the therapy after local recurrence and second (non-breast) cancer (as during the trial we clarified that we considered protocol therapy as ended at the DFS event in such cases as well); such therapy is *not* considered as non-protocol therapy for these analyses.

Also in SOFT, if a patient had been on tamoxifen and was randomized to Exe+OFS, the tam was allowed to continue until the exe was started, 6-8 weeks after OFS was initiated; this is also captured on the Treatment Summary form non-protocol therapy page and such therapy is *not* considered as non-protocol therapy for these analyses.

With regard to non-protocol OFS:

- At the time of this database lock, there was no record of non-protocol ovarian irradiation use;
- Any use of GnRH agonist is considered, of any type, and for any duration (as long as not after DFS event);
- Any ooph reported >5yrs for any reason is recorded, as long as it's not after DFS event;
- The timing of non-protocol OFS was segmented as 0 to 4.5yr since randomization vs.  $\geq 4.5$ yr since randomization; this is in parallel with protocol therapy, for which triptorelin through 4.5yr was considered as completed per protocol.

With regard to non-protocol ET:

- As noted, it can be difficult to differentiate competing 5 yrs of oral ET from extended oral ET use from the 66 month visit; the plan is to identify number of patients on oral ET at  $\geq 6$  yrs since rando; look at 2 denominators, ITT, and patients who are DFS event-free & in follow-up at 6 yrs since rando.
- There is just one record of toremifene, which is just being lumped with tamoxifen
- 

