#### **1.3.2 OFS Question**

After a median follow-up of 67 months (5.6 years), DFS events were reported for 299 (14.7%) of 2033 patients in the ITT population. T+OFS non-significantly reduced hazard of a DFS event vs. T (HR=0.83; 95% CI, 0.66 to 1.04; P=0.10). The estimated 5-year DFS among patients assigned T+OFS was 86.6% (95% CI, 84.2% to 88.7%) versus 84.7% (95% CI, 82.2% to 86.9%) among patients assigned T. The relative effects of T+OFS vs. T were consistent between the two chemotherapy strata; as expected, the absolute difference at 5 years was more notable among patients who received prior chemotherapy. The reduction in hazard with T+OFS vs. T was consistently observed for the secondary endpoints of breast-cancer-free interval and distant recurrence-free interval. 106 (5.2%) deaths were reported, and on average there was a non-significantly reduced hazard of death; with all except 10 deaths among patients who received prior chemotherapy, the reduction in hazard was more apparent among this cohort of patients

At the time of the analysis, 26% of patients continued on protocol-assigned treatment. 31% and 24% of patients assigned to T+OFS and T have had grade 3-5 targeted AEs reported, of which hot flashes/flushes, musculoskeletal symptoms and hypertension were the most frequently reported.

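### Must the update report show how many tamoxifen-alone patients received ovarian suppression, and does the 4.5-year split spoil that count?

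*SAP*

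**What the plan says.** SAP 2.5 compares disease-free survival (DFS) between tamoxifen plus OFS (T+OFS) and tamoxifen alone (T) by stratified logrank test. It reports a stratified Cox hazard ratio (HR) and 8-year DFS. SAP 2.2 (Analysis Populations) keeps the intention-to-treat (ITT) approach.

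SAP 2.6.6.2 covers non-protocol treatment and opens with "This will not be part of the update clinical trial report". It goes on to announce a preliminary analysis once the report has been compiled, and adds that "a full analysis of protocol and non-protocol treatment is planned to follow separately". One of the items to be described there, marked for the OFS question, is "Use of OFS within 5 years of randomization among patients assigned tamoxifen-alone".

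The same section gives several counting rules:

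- GnRH agonist use of any type and any duration counts, provided it comes before a DFS event.
- For late oophorectomy: "Any ooph reported >5yrs for any reason is recorded, as long as it's not after DFS event".
- For timing: "The timing of non-protocol OFS was segmented as 0 to 4.5yr since randomization vs" 4.5 years or later. The reason given is that "this is in parallel with protocol therapy, for which triptorelin through 4.5yr was considered as completed per protocol".
- For irradiation: "At the time of this database lock, there was no record of non-protocol ovarian irradiation use".

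SAP 2.6.6.3 keeps treatment status and cumulative early discontinuation by treatment group in the outputs.

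**The concern.** SOFT is not blinded. SAP 1.2.3 expected the first results in mid-2014 (AI question) and late 2014 (OFS question), and SAP 1.3.2 records of the OFS-question population: "At the time of the analysis, 26% of patients continued on protocol-assigned treatment". Some tamoxifen-alone patients could therefore have learned the results and started OFS inside their own five years. The update, with visits to 31Dec16 (SAP 2.4), is the first analysis to include that period. OFS taken in the control arm pulls the ITT hazard ratio toward 1. A reader shown only the hazard ratio cannot see how much of a weak effect is dilution. The plan treats the quantity as relevant to this question, yet reports the estimate without it.

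The timing rules look inconsistent as well. The item covers use within 5 years, while the split is at 4.5 years and is borrowed from a completion rule for triptorelin that patients assigned tamoxifen alone never had. OFS started between 4.5 and 5 years falls in the later segment together with post-5-year use, and the section does not say how it feeds the within-5-years item. If the early segment were taken as the answer to that item, contamination would be undercounted.

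**Working it through.** **The plan's own figures.** The documents state no crossover rate, so there is no contamination figure to reproduce. The nearest stated figure is the power for T+OFS versus T in SAP 1.2.3: 80%, 69%, 52% and 34% at HR 0.665, 0.70, 0.75 and 0.80, two-sided 0.05, with about 93 events per group (186 for two arms). With power = Φ(√186/2 × |ln HR| − 1.96) I get 79.5%, 68.2%, 50.1% and 33.1%, all within 2 points. For HR 0.75: 6.819 × 0.2877 − 1.96 = 0.002, hence 50.1%.

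**Dilution.** Suppose a share f of the control arm has OFS with full effect from randomisation. This is an upper bound, because real starts come later. Then

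HR seen = HR / ((1 − f) + f × HR).

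| Assumed f | True HR 0.80 | True HR 0.75 |
|---|---|---|
| 5% | 0.80/0.990 = 0.808 | 0.75/0.9875 = 0.759 |
| 10% | 0.80/0.980 = 0.816 | 0.75/0.975 = 0.769 |
| 20% | 0.80/0.960 = 0.833 | 0.75/0.950 = 0.789 |
| 25% | 0.80/0.950 = 0.842 | 0.75/0.9375 = 0.800 |

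The shift is at most 0.04 up to f = 20%, and 0.05 at 25%.

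**Against the precision.** The first OFS-question result was HR 0.83, 95% CI 0.66 to 1.04, on 299 events (SAP 1.3.2). The standard error of log HR is (ln 1.04 − ln 0.66)/(2 × 1.96) = 0.116. At f = 20% and true HR 0.75 the log shift is −ln(0.95) = 0.051, and 0.051/0.116 = 0.44 standard errors. More events at the update will narrow the interval, so the ratio will grow. If the events were to double (an assumption), the standard error would be 2/√598 = 0.082 and the ratio 0.051/0.082, or about 0.63. At 299 events, power for a true HR of 0.75 falls from 70% to between 66% (f = 5%) and 49% (f = 25%).

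**The 4.5-year split.** The segments are 0 to 4.5 years and 4.5 years or later. Together they cover all follow-up, so no use is left out. What matters is how much falls between 4.5 and 5 years:

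- If first OFS use is assumed uniform over 0 to 5 years, the share of users is 0.5/5 = 10%.
- Their share of within-5-year OFS time is (0.5²/2)/(5²/2) = 1%.
- If starts are front-loaded, with an assumed half-life of 1 or 2 years, the share of users is 1% or 4%.
- The T arm holds about 2033/2 ≈ 1,017 women. With 5% to 25% of them starting OFS within five years, the band holds 1,017 × 0.05 × 0.10 ≈ 5 to 1,017 × 0.25 × 0.10 ≈ 25 women.

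**Release of results.** The last SOFT patient was randomised on 27Jan11 (SAP 1.2), so every five-year window closed by late January 2016. For results expected from mid-2014, only patients randomised from about mid-2009 were still inside their window, and late in it. The 26% still on treatment pools both arms and refers to the 31Mar14 cut-off, before the expected release. It is not a rate of exposure to the results in the control arm.

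**The case for a change.** The best case for a change is that the count is cheap and belongs beside the estimate. The section already reports a finding at this database lock, that no non-protocol irradiation was on record, so the forms have been examined. Protocol 3.2.6 excludes women likely to be advised oophorectomy within five years, which shows that the designers saw control-arm OFS as a threat. With a first HR of 0.83, a modest dilution matters to interpretation: if 20% of the control arm had been fully treated, the undiluted value would be 0.83 × 0.80/(1 − 0.83 × 0.20) = 0.796. The retained treatment tables are not described as showing OFS started in the tamoxifen-alone arm.

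It stands that readers of the update will not have this count in front of them, and that the handling of starts between 4.5 and 5 years is not spelled out. It does not stand that the information is dropped: it is scheduled, and this item is named. Nor is a miscount shown. The split is a descriptive segmentation with a stated reason, namely to cut protocol and non-protocol OFS at the same time, and a within-5-year count can be made from start dates if these are held.

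A supportive model that censors at first OFS, with inverse-probability weights, would need time-varying predictors of starting OFS. The documents do not show that these are available. The gain over a plain ITT estimate is therefore debatable.

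**Conclusion.** No change to the plan follows. The objective is an ITT comparison of assigned strategies. Its hazard ratio, test and confidence interval are the same whether or not a crossover table sits beside them. Placing that table in a separate treatment paper is a fair trade-off. SAP 2.6.6.1 reports that the Treatment Summary form was completed inconsistently around year five. That inconsistency concerns oral therapy, mainly in TEXT, but it supports a careful separate pass over the treatment data.

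The differing 4.5-, 5- and over-5-year boundaries are a gap in wording that an analyst would fill by counting from start dates. I do not judge which completion rule for triptorelin is right. The split affects a description only and enters no efficacy model.

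Dilution at assumed crossover of 5% to 20% moves the HR by at most 0.04, small against a first-report interval of 0.66 to 1.04, and it could not make a true 0.80 look like no effect. The assumptions are that crossover is no greater than the range shown, that OFS starts are spread no later than uniformly over five years, and that start dates are held. The original SAP, to which this one refers, was not available, so I could not check whether control-arm OFS use was covered there.
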